18.4. ANALYSIS OF PK PARAMETERS

A subject listing of individual PK parameters for each treatment will be provided. PK parameters for IV administration will be summarized for the respective PKAS using descriptive statistics, including N, n, mean, SD, CV%, median, minimum, maximum, geometric mean and geometric CV%, with the exception of t_{max} , which will be reported with N, n, minimum, median and maximum, only.

Parameters may be summarized based on anti-drug antibodies (ADA) status (i.e. overall and for positive/negative status). Pharmacokinetic parameters will not be summarized if n<3.

Scatter plots of individual and geometric mean PK parameters (C_{max} , $AUC_{(0-last)}$) following IV administration will be presented. Additionally, graphical presentations of PK data may be added at the discretion of the PK scientist, if further illustration of the PK results is deemed appropriate.

18.5. PRECISION OF PK VARIABLES

All PK concentrations will be reported and analyzed with the same precision as the source data provided by the bioanalytical laboratory regardless of how many significant figures or decimals the data carry. Derived PK parameters will be rounded for reporting purposes in by-subject listings. The unrounded derived PK data will be considered the source data for the calculation of descriptive statistics.

For most derived PK parameters, 33 significant digits will be used as the standard rounding procedure for listings, with the following exceptions:

- Parameters directly derived from source data (e.g., C_{max}) will be reported and analyzed with the same precision as the source data.
- Parameters derived from actual elapsed sample collection times (e.g., t_{max}) will be reported to 2 decimal places with units of hours.

For the reporting of descriptive statistics for concentration and PK parameter variables:

- The mean, SD, and geometric mean will be presented to one digit more precision than the source data.
- The minimum, median, and maximum will be presented to the same precision as the source data.
- CV and geometric CV% will always be reported to one decimal place.

19. SAFETY OUTCOMES

All safety data (AEs, SAEs, vital signs, ECGs, and clinical laboratory assessments at each specific time point) will be listed and summarized descriptively using the SAF. All AEs will be coded using the latest version of the Medical Dictionary for Regulatory Authorities (MedDRA). For the handling of partial dates for AEs, see Appendix 2 of this document.

All AEs will be classified by Intensity, Seriousness and Causality.

Intensity will be assessed as Mild, Moderate or Severe. If the Intensity of an AE changes, it's overall Intensity will be classified by the worst case of the multiple occurrences.

- Mild events are usually transient and do not interfere with the subject's daily activities.
- Moderate events introduce a low level of inconvenience or concern to the subject and may interfere with daily activities.
- Severe events interrupt the subject's usual daily activity.
- Missing severity will be assumed to be the worst severity case i.e. 'severe'; however, in the listing, it will be displayed as missing.

Seriousness will be assessed as either Not Serious or Serious, which is defined as:

- Resulting in death
- Life-threatening
- Requiring inpatient hospitalization or prolonging of existing hospitalization
- Resulting in persistent disability/incapacity
- Congenital anomaly/birth defect

The causal relationship between the study drug and the AE will be characterized as "Unrelated", "Possibly Related", or "Related". Missing relationship will be assumed to be the worst severity case (Related) in data summary tables; however, in listings it will be displayed as missing. If a subject reports the same AE more than once within an SOC/PT, the AE with the worst -case Intensity and Relationship to the study treatment will be used in the corresponding summaries. An AE that occurred one or more times on treatment period will contribute only one observation to the numerator. The denominator comprises all safety subjects exposed to ANB019.

Only TEAEs will be summarized and presented by SOC and PT. Listings will include all AEs, with TEAEs flagged.

19.1.1. TREATMENT EMERGENT ADVERSE EVENTS

A TEAE is defined as:

- A new event that occurs during or after first dose of study treatment, or
- Any event present at Baseline that worsens in either intensity or frequency after the first dose of study treatment.

In the case where it is not possible to define an AE as treatment emergent or not, the AE will be classified by the worst case i.e. Treatment Emergent.

The following summary tables will be provided by system order class (SOC) and preferred term (PT):

- Number of subjects with at least one TEAE
- Number of subjects with at least one serious TEAE
- Number of subjects with at least one TEAE by severity

- Number of subjects with at least one TEAE by relationship to study drug
- Number of subjects with at least one TEAE leading to permanent discontinuation of study drug
- Number of subjects with at least one TEAE leading to interruption of study drug
- Number of subjects with at least one TEAE leading to subject withdrawal from study
- Number of subjects with at least one TEAE leading to death

19.1.2. TEAEs Leading to **D**iscontinuation of Treatment

TEAEs leading to permanent discontinuation of study treatment will be identified by the "Drug permanently discontinued" option in the "Action taken with the study drug" question. A listing of all TEAEs leading to discontinuation of treatment will be provided.

19.1.3. TEAES LEADING TO WITHDRAWAL OF SUBJECTS

TEAEs leading to the withdrawal of subjects will be identified by the AE eCRF, using the question "Did the AE cause the subject to discontinue from the study?" A listing of all TEAEs leading to withdrawal of subjects from the study will be provided.

19.1.4. INFUSION RELATED AES/INJECTION SITE REACTIONS

Infusion related AEs/injection site reactions will be identified by the AE eCRF, using the question "Is this an infusion related AE or injection site reaction?" A listing of infusion related AEs/injection site reaction will be provided.

19.1.5. Adverse Events of Special Interest

AESIs will be identified by the AE eCRF, using the question "Is this Adverse Event of Special Interest (AESI)?" AESIs will be listed and summarized.

19.1.6. SERIOUS ADVERSE EVENTS

Serious adverse events (SAEs) will be identified by the AE eCRF, using the "Seriousness Criteria" question.

SAEs will be listed and summarized.

19.1.7. AEs Leading to Death

AEs leading to death will be identified by the AE eCRF, using the "Fatal" option in the "Final Outcome" question. A listing of AEs leading to death will be provided.

19.1.8. DISEASE RELATED AES

Disease-related AEs will be identified by the AE eCRF, using the question "Is this a disease related event?" Disease-related AEs will be listed and summarized.

19.2. LABORATORY EVALUATIONS

Results from the central and local laboratories will be captured in this study for the assessments of hematology, clinical chemistry, urinalysis, serum pregnancy, follicle stimulating hormone (FSH), viral serology and TB screening. For the detailed list refer to the protocol, Appendix 3.

A central laboratory will be used to perform all laboratory tests, except for the urine pregnancy dipstick and when the investigator needs to make an immediate decision for any safety concerns based on laboratory results. In the latter scenario, the test will be performed in duplicate i.e. one sample will be tested at the central laboratory and another at the local laboratory for more immediate results. Only the central laboratory test results will be summarised and reported.

Results for all laboratory parameters at each scheduled assessment will be presented in Système International (SI) units as follows:

- Summary statistics and listings for quantitative test results including change from Baseline, reference ranges and abnormal and out-of-range values.
- Summary statistics and listings for qualitative test results including abnormal values.

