Treatment-related effects observed in the 13-week, repeat-dose toxicity study included protozoa in the stomach, an increase in nonformed feces and prolapsed rectum observations, the latter was not dose-related. The increase in protozoa in the stomach has been observed in monkeys treated with immune-modulating drugs (Augey 2006) and is consistent with the putative mechanism of action of ANB019. The increased incidence of protozoa, nonformed feces and prolapsed rectum were not considered adverse as they responded to veterinarian intervention. Gastrointestinal infections are clinically monitorable and, in the case of most protozoa, are readily treatable even in the context of immunocompromised individuals (Farthing 2006). One female monkey receiving 60 mg/kg ANB019 IV was found moribund on Study Day 34. The cause of the moribund nature was not determined and had an uncertain relationship to ANB019 but could be due to treatment-related immune-modulation. However, data published on IL-36 R deficient humans shows no deleterious effect on general health and normal immune function broadly preserved, indicating that inhibition of IL-36 R, apart from disease modification, does not compromise host defenses. Similar to other immune-modulating treatment paradigms, subjects should be closely monitored for any gastrointestinal clinical manifestations including infections and evaluated on ongoing basis. If a gastrointestinal infection is suspected, the subject should be treated as clinically indicated.

As allergic or anaphylactic reactions may occur in subjects treated with mAbs, subjects should be observed during and after study drug administration. Subjects with true allergic/anaphylactic reactions should not receive further doses of the product.

As ANB019 is an mAb, based on clinical studies with other mAbs, study participants may experience symptoms of an apparent allergic reaction to the drug, also known as ‘cytokine release syndrome.’ The symptoms of this vary dramatically but can include:

- Mild to moderate fever, chills, headache, nausea, and vomiting.

- Moderate to severe signs and symptoms such as edema, hypotension, and pulmonary infiltrates (eg, blood and mucus in the lung).

Such reactions should be managed as clinically indicated and according to standard clinical practice.

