### **8.2.7 Clinical Safety Laboratory Assessments**

- See [Appendix 3](#) for the list of clinical laboratory tests to be performed and to the Schedule of Activities (see Section 1.3) for the timing and frequency of the tests.
- A central laboratory will be used to perform all laboratory tests except urine pregnancy dipstick which will be assessed by the center staff. However, local laboratory tests will be allowed in the event that the central laboratory results will not be available immediately and the Investigator needs to take an immediate decision for any safety concerns based on laboratory results.
- The Investigator must review the laboratory report, document this review, and record any clinically relevant changes occurring during the study in the AE section of the case report form. The laboratory reports must be filed with the source documents. Clinically significant abnormal laboratory findings are those that are not associated with the underlying disease, unless judged by the Investigator to be more severe than expected for the subject's condition.
  - All laboratory tests with values considered clinically significantly abnormal during participation in the study including the subject's last EOS visit should be repeated until the values return to normal or baseline or are no longer considered clinically significant or judged medically stabilized by the Investigator or Medical Monitor.
    - If such values do not return to normal/baseline within a period of time judged reasonable by the Investigator, the etiology should be identified and the Sponsor notified.
    - All protocol-required laboratory assessments, as defined in [Appendix 3](#), must be conducted in accordance with the Laboratory Manual and the Schedule of Activities (see Section 1.3).
    - If laboratory values from non-protocol specified laboratory assessments performed at the institution's local laboratory require a change in subject management or are considered clinically significant by the Investigator (eg, SAE or AE or dose modification), then the results must be recorded in the eCRF.

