#### **9.4.5.2 *Physical Examinations, 12-Lead ECG, Vital Signs and Clinical Safety Laboratory Tests (Hematology, Biochemistry, and Urinalysis)***

Summaries and listings of data for both limited and complete physical examination findings, vital signs, hematology, biochemistry, and urinalysis laboratory tests will be presented. Appropriate descriptive statistics will be summarized for the observed value at each scheduled assessment and for the corresponding change from Baseline.

For hematology and biochemistry tests, listings of subject data will also flag up any abnormal or out-of-range values. Clinically significant changes in the laboratory test parameters will be summarized and listed. Hematology and clinical laboratory data will be reported in System International units.

Descriptive statistics will be used to present the safety outcomes including, physical examination results, weight, BMI, 12-lead ECG, vital signs measurements, and clinical laboratory test results.

Change from Baseline will also be summarized for vital signs measurements, clinical laboratory test results.

All ECG data results (normal/abnormal) will be summarized using frequency and percentages. Clinically significant abnormalities will be presented in by subject listings.

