5.4. CHANGES TO ANALYSIS FROM PROTOCOL

There are no changes from the analysis mentioned in the protocol.

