8.3. RETESTS, UNSCHEDULED VISITS AND EARLY DISCONTINUATION

In general, for by-visit summaries and figures, data recorded at the nominal visit will be presented. In the

event of a retest of the same sample due to e.g. a laboratory error (same visit number assigned), the last usable assessment will be used. Unscheduled measurements will not be included in by-visit summaries, but will contribute to the Baseline, EOS, End of Treatment (EOT) and Last Observation Carried Forward (LOCF) values, or best/worst case value where required (e.g. shift tables).

Listings will include scheduled, unscheduled and early discontinuation data, with unscheduled visits sorted chronologically.

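### The SAP names no summary of clinically significant laboratory changes, which protocol 9.4.5.2 requires, and its central-only sentence would leave unpaired local results unreported

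*SAP*

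**What the plan says.** Protocol 9.4.5.2 plans descriptive statistics at scheduled assessments, listings that flag abnormal values, and one further output: "Clinically significant changes in the laboratory test parameters will be summarized and listed".

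SAP 19.2 is organised by scheduled visit: "Results for all laboratory parameters at each scheduled assessment will be presented in" SI units, as summary statistics and listings. When a local test is done for an immediate safety decision, "one sample will be tested at the central laboratory and another at the local laboratory for more immediate results". The next sentence is "Only the central laboratory test results will be summarised and reported". SAP 19.2.2 defines Low, Normal and High but attaches no table to these categories.

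SAP 8.3 says "Unscheduled measurements will not be included in by-visit summaries". It lets such values contribute to Baseline, EOS, EOT and LOCF values, and to best or worst values where an output needs them (shift tables are its example). It also keeps them in listings.

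Protocol 8.2.7 covers local tests outside the protocol panel. If these change subject management or are judged clinically significant, "then the results must be recorded in the eCRF".

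SAP 5.4 states: "There are no changes from the analysis mentioned in the protocol".

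**The concern.** Hematology, biochemistry and urinalysis are part of the primary safety endpoint in both documents. Off-schedule values are foreseen, since protocol 8.2.7 requires clinically significant results to be repeated until they normalise, return to baseline or stabilise. The protocol's summary of clinically significant changes is the natural place for such values to be counted, and the SAP text does not carry it over.

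A separate difficulty is the word reported in the central-only sentence. It reaches beyond tables to listings, and so conflicts with rules elsewhere in the protocol and SAP.

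At stake is whether a reader of the laboratory tables would see the most extreme value that a subject had, and whether every laboratory result that drove a decision can be found in the report.

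**Working it through.** The documents give no figure to reproduce. The check sets the texts side by side.

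1. **Scheduled-visit statistics.** Protocol 9.4.5.2 asks for observed values and change from Baseline at scheduled assessments. SAP 19.2 provides these. The two agree.

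2. **Clinically significant changes.** Protocol 9.4.5.2 asks for a summary and a listing. SAP 19.2 offers summary statistics and listings that include abnormal and out-of-range values. Nothing in 19.2, 19.2.1 or 19.2.2 counts or tabulates clinically significant changes. The summary is missing, and the listing is met only so far as abnormal values are shown. By contrast, SAP 19.3 specifies for ECG both a shift from Baseline and a listing of clinically significant abnormalities.

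3. **Path of an unscheduled central value after baseline.**
   - By-visit summary: excluded by SAP 8.3.
   - Worst-case or shift table: admitted by SAP 8.3 only where such a table is required, and SAP 19.2 requires none.
   - EOS, EOT or LOCF value: possible, but these take a late or carried value and not a peak.
   - Listing: included.

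   The value is listed, but no laboratory table is assured to contain it.

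4. **Path of a local value.**
   - Immediate-decision test on the central panel: SAP 19.2 and protocol Appendix 3 both call for a central sample at the same time. The central twin is reported, although a twin taken off schedule falls under step 3.
   - Test outside the protocol panel: protocol 8.2.7 sends certain results to the eCRF, and no central pairing is stated. Under the central-only sentence such a value is neither tabulated nor listed. Protocol 9.4 says all data go into by-subject listings, and SAP Appendix 1 says eCRF variables with data should be listed. These instructions cannot all be followed.

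5. **Declared changes.** SAP 5.4 declares none, so the omission in step 2 is not presented as a decision. The SAP was written to Amendment 4, but this does not explain the gap: the log for Amendment 5 reports only a change to laboratory eligibility and minor edits.

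**The case against.** The strongest reply is that the central-only sentence is a sensible de-duplication rule. It directly follows the description of duplicate testing, and for panel tests it gives one result under one set of reference ranges. That stands, and the by-visit tables should keep it. It does not cover tests without a twin.

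A second reply is that clinically relevant changes must be recorded in the AE section (protocol 8.2.7), so they reach the TEAE, SAE and AESI tables. That also stands, and it limits the harm. But AE tables show events, not values or shifts. Under protocol Appendix 4, abnormalities attributed to the underlying disease are not AEs unless more severe than expected. The AE route therefore does not replace the promised laboratory summary.

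A third reply is that with about 10 subjects and no hypothesis testing, listings can be read in full. True, but the protocol asks for a summary as well.

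A reader might infer more than the documents support:

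- *That the SAP contradicts protocol 8.2.7.* It does not. That section governs review, recording and repeat testing, and sets no rule for tables.
- *That restricting by-visit statistics to scheduled visits departs from protocol 9.4.5.2.* It does not; the protocol has the same restriction.
- *That the visit gaps measure what is lost.* Scheduled laboratory days are 1, 3, 8, 15, 22, 29, 43, 57, 71, 85, 113, 141 and 169. The gaps are 2, 5, 7, 7, 7, then 14 four times and 28 three times, summing to 168. Assuming uniform onset, a 7-day abnormality would meet a scheduled sample with probability (2 + 5 + 10 × 7)/168 = 77/168 = 46%. Within Days 1 to 29 it is 28/28 = 100%, and after Day 29 it is 49/140 = 35%. This describes sampling density. An episode with no sample is unobserved under any reporting rule, so the figure says nothing about values removed by the SAP.
- *That the tables are shown to be biased towards safety.* Omitting unscheduled peaks creates that risk, but without a rate of such samples no bias is demonstrated.

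**Conclusion.** The point holds as two specific gaps. First, the summary of clinically significant laboratory changes required by protocol 9.4.5.2 is absent from SAP 19.2 to 19.2.2. No shift or worst post-baseline table takes its place, and SAP 5.4 declares no change. Second, the central-only sentence, read literally, conflicts with the listing rules in protocol 9.4 and SAP Appendix 1 and would leave unpaired local results unreported.

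The size cannot be stated as a number. It depends on how many unscheduled and unpaired local tests occur, which the documents do not give. It matters mainly because the study is small: among about 10 subjects, one abnormality is roughly 1/10 = 10% of the sample. SAP 7.1 plans no Data Monitoring Committee, and SAP 7.2 has all safety data assessed at the interim analysis.

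The conclusion rests on the SAP text. SAP section 10 refers to templates that fix the content of tables and listings, and these were not available. If they already contain the summary and a laboratory shift table, the first gap reduces to missing text in 19.2. This should be corrected before database lock; nothing in it bears on clinical management.

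**What to change.** In SAP 19.2:

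1. Keep central results at scheduled visits for the by-visit tables. Confine the central-only sentence to by-visit summaries where a test was run in duplicate.
2. Add a summary and a listing of clinically significant laboratory changes, including unscheduled central results. State where the clinically significant classification comes from: the documents describe investigator review and AE recording, but do not say whether the laboratory data carry such a field.
3. Add a shift from Baseline to worst post-baseline value, using the Low, Normal and High categories of 19.2.2 and including unscheduled central results as SAP 8.3 already permits.
4. List all local results recorded in the eCRF, flagged by source and classified against their own reference range. A listing is the right place for tests outside the protocol panel, which have no scheduled baseline and so generally cannot enter a shift table.

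If the templates already hold these outputs, refer to them in 19.2. If the sponsor chooses not to produce the summary, SAP 5.4 should declare the change.

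The cost is a short SAP revision, two tables and the listings. The values themselves are already collected. The one drawback is that local results rest on differing reference ranges, which the source flag and a footnote deal with.

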19.2.1. LABORATORY SPECIFIC DERIVATIONS

Quantitative laboratory results reported as "< X", i.e., below the lower limit of quantitation (BLQ), or "> X", i.e. above the upper limit of quantitation (ULQ), will be converted to X for quantitative summaries, but will be presented as recorded, i.e., as "< X" or "> X" in the listings.

